8. PARTICIPANT IDENTIFICATION

WS2 – Participants, Inclusion and Exclusion Criteria

Study Participants

Patients aged over 18 attending the Emergency Departments and admitted as inpatients who are included in the scope of the alert in each trust.

From the hospital population we will identify patients aged between 18 and 110 who attend the Trust and lie within the scope of the alert. The scope of the alert will vary between Trusts, for example at ICHNT patients who are attend maternity wards and outpatient clinics are not currently included in the alert scope.

Inclusion Criteria

Patients who, on discharge or death, have an ICD-10 code included in the list of codes identified as Suspicion of Sepsis used in the Sepsis Insight Dashboard [www.sos-insights.co.uk]; Patients who 'alerted' - this is a binary indicator within electronic health records, this will depend on system the Trust uses to identify patients at risk of sepsis and/or deterioration related to sepsis. In order to carry out sensitivity analysis we will extract clinical information for patients with an ICD-10 code related to a condition as identified as being appropriate to the local health economy.

Exclusion Criteria

There are no pre-registration evaluations, no specific inclusion and exclusion criteria are there is no withdrawal from the study.

WS3 – Participants, Inclusion and Exclusion Criteria

Study Participants

Participants will include hospital healthcare professionals and patients/carers in the UK. The sample size will depend on saturation³³⁻³⁴, i.e. no new themes are identified in data from later interviews/focus groups, however it is estimated that around 25 healthcare professionals and 20 patients/carers will participate.

Analysis of data from the interviews and the focus groups will occur concurrently to data collection, where possible, to inform future sampling and data collection.

Inclusion Criteria

- Participant is willing and able to give informed consent for participation in the study.
- Any gender aged 18 years or above (no upper age limit).
- Fluent in English (or able to participate in an interview with other measures in place, e.g. interpreter).
- For clinicians: Currently working as a healthcare professional (e.g. doctor, nurse) in an NHS hospital trust.
- For patients/carers: Member of the public who has previously been diagnosed with sepsis and treated in hospital or carer/relative of someone who has previously had sepsis.

Exclusion Criteria

The participant may not enter the study if ANY of the following apply:

• Healthcare professional has less than 3 months experience working in relevant role. This is estimated to be a reasonable amount of time for them to have good experience of identifying patients with sepsis and/or using sepsis alert systems.

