2.2 Participants

All adult (18+) inpatients admitted between 01/02/19 and 31/01/21 are initially eligible for inclusion in the study. We will liaise with data managers at each NHS Trust and identify all patients who triggered a sepsis alert in each Trust. The sample of patients included in the study are adult inpatients who triggered a sepsis alert at any point in their inpatient stay or time in A&E in the 24 months of the study.

The NHS Trusts included in the study are of differing sizes and may differ in case mix. In order to compare hospitals we will use patients with a serios infection, and therefore at risk of sepsis to adjust outcomes for patients with an alert. In order to identify patients with a serious infection will use the ICD-10 codes suggested by Inada-Kim et al and classed as 'Suspicion-of-Sepsis' (SoS). Patients are identified if a patient has an SoS ICD-10 code at discharge or at death.

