2.3 Variables

The main aim of this study is to describe and quantify differences in patients who alert in different NHS Trusts. The 'key exposure' is the algorithm used to define the sepsis alert in the five NHS Trusts. Variables of interest are identified in Table 2.

Table 2 Empty table to illustrate proposed data collection for Study 1. Superscript numbers refer to specific questions shown at the end of the document.

NHS Trust	Α		В		С		D		Е	
Sepsis alert algorithm	Red Flag	SoS	NEWS2	SoS	Red Flag	SoS	Oxford's alert	SoS	SJSA	SoS
Frequency										
Total Number of alerts in 12										
months										
Seasonal variation in alerts										
Shift (time) of alert ¹										
Patient characteristics ²										
%Male										
Age – median and IQR										
Ethnicity										
Comorbidities ³ /Conditions on										
discharge										
>Diabetes										
> Immuno-compromised										
Deprivation										
Location of alerts ⁴										
%ED										
%other key wards										
Process measures ⁵										
Received IV antibiotics										
Received IV antibiotics within 3		NA		NA		NA		NA		NA
hrs of alert										
Blood test ordered										

Blood test ordered within 3 hrs	NA	NA	NA	NA	NA
of alert.					
Lactate measurement					
Lactate measurement within 3	NA	NA	NA	NA	NA
hrs of alert					
Outcomes					
Length of stay for those who					
alert in the ED					
Admission to ICU after alert					
Mortality – 7 days					
Mortality – 30 days					
Impact on coding/formal					
diagnosis					
Proportion with a sepsis code at					
discharge/death					
Proportion with a SoS code at	NA	NA	NA	NA	NA
discharge/death					
Alert specific response	NA	NA	NA	NA	NA

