2.5 Bias

In order to compare the impact of different algorithms on the characteristics and patterns of alerting, the case-mix being admitted to the hospital is the key source of bias. All hospitals are in a similar region of England, but the intake of the five hospitals is different in terms of ethnicity, age and deprivation. In order to determine if the algorithm is the key factor determining differences in the profiles of the patients who alert we compared the profile with patients discharged with an ICD-10 SoS code.

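### The five-Trust algorithm comparison does not settle whether alert scope, which differs by Trust, limits its comparators and denominators, and does not name scope as a bias

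*Protocol*

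**What the plan says.** Protocol section 8 (WS2, Study Participants) takes adults "who attend the Trust and lie within the scope of the alert" and adds: "The scope of the alert will vary between Trusts, for example at ICHNT patients who are attend maternity wards", who, like outpatient clinics, are described as not currently covered at that Trust. No other Trust's scope is described. The same section lists both SoS-coded and alerting patients as inclusions.

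The first Appendix study (comparison of alerting algorithms) opens differently. Its section 2.2 says "All adult (18+) inpatients admitted between 01/02/19 and 31/01/21 are initially eligible for inclusion in the study". The analysed sample is "adult inpatients who triggered a sepsis alert at any point in their inpatient stay or time in A&E". SoS comparators are found by an ICD-10 code at discharge or death, with no restriction on ward or scope. Section 2.3 states: "The 'key exposure' is the algorithm used to define the sepsis alert in the five NHS Trusts". Section 2.5 says that "the case-mix being admitted to the hospital is the key source of bias", and the remedy offered is that "we compared the profile with patients discharged with an ICD-10 SoS code".

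For scaling, Appendix section 3.1 uses overnight beds and SoS admissions, and section 7.2 uses inpatient admissions and A&E attendances. None of these is stated to be limited to in-scope areas.

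**The concern.** The areas where an alert is switched on are a deployment choice, not a property of the score. The rationale of the first Appendix study considers two explanations for differences between Trusts, algorithm and intake. Scope is a third, and the protocol itself says that it varies.

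According to Appendix Table 1, SJSA is used only at ICHT, the one Trust whose scope is described as narrower. At that Trust scope and algorithm coincide, so neither patient covariates nor Trust-level clustering can separate them: no model supplies alerts from wards where the alert was not live. The findings also feed Workstream 4, which aims to identify the most effective alert (objective 4.1).

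This is not detail left to another document. Section 10 places the detailed statistical plans in the Appendix, and the bias section there is written out without scope.

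**Working it through.** The protocol gives no sample size, power or out-of-scope share for this comparison, so there is no planned figure to reproduce. The check sets the two population rules side by side and then illustrates the size.

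**Step 1: which rule applies to what**

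| | Section 8 rule (own scope) | Appendix 2.2 rule (all adult inpatients) |
|---|---|---|
| SoS comparators | in-scope patients only | include patients who could not alert |
| Admission denominators | in-scope | whole Trust |
| Raw profile of alerting inpatients | own scope, differs by Trust | own scope, differs by Trust |

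The text does not say which rule governs the five-Trust comparison. The last row is the same under both.

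**Step 2: alert rate**

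Assumptions: two Trusts use the same algorithm. At Trust W everything is in scope. At Trust N a share m of SoS admissions lies out of scope. Alerts per in-scope SoS admission equal r at both.

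- Whole-Trust denominator: W has rate r and N has r(1 - m), so the apparent rate ratio (RR) is 1 - m.
- In-scope denominators: RR = r/r = 1.00.
- In-scope denominators, with alert propensity in the extra areas k times that elsewhere: RR = 1/[(1 - m) + mk]. At m = 5%, k = 0.5 gives 1/0.975 = 1.03, and k = 2 gives 1/1.05 = 0.95.

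**Step 3: patient profile**

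Assume 50% male among alerts at W, with a share m of W's alerts coming from the extra areas and all of those patients women. Percent male at N is then 0.50/(1 - m).

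**Step 4: when it would be flagged**

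Appendix section 3.1 uses a threshold of 0.01; 80% power is assumed.

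- Rate ratio: n = (2.576 + 0.842)² × (1 + 1/RR)/(ln RR)², where n is the number of alerts at W. At m = 5%: 11.68 × 2.0526/0.002631, about 9,100.
- Percent male: the usual two-proportion formula, with pooled variance under the null.

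| m | apparent RR, whole-Trust denominator | % male at N (50% at W) | alerts to flag RR | alerts per Trust to flag % male |
|---|---|---|---|---|
| 1% | 0.99 | 50.5 | 232,400 | 228,900 |
| 2% | 0.98 | 51.0 | 57,800 | 56,100 |
| 5% | 0.95 | 52.6 | 9,100 | 8,400 |
| 10% | 0.90 | 55.6 | 2,200 | 1,900 |

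**Step 5: what is not affected**

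ED alerts divided by A&E attendances do not involve maternity wards. Outpatients are outside the Appendix sample at every Trust.

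**The case against.** The strongest defence is that section 8 defines the Workstream 2 population and this study serves Workstream 2 objectives, so the SoS patients are already in scope. The plan then has a working safeguard: Table 2 sets an SoS column beside every alert column, and section 3.1 adjusts between hospitals using SoS patients. ED and inpatient alerts are separated, and Workstream 1 records local adaptations. The SoS offset in the Poisson model is stated for contrasts of shift, weekday and season, where a stable out-of-scope share largely cancels. The study calls itself mainly descriptive, and describing each alert as deployed is legitimate.

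Much of this stands. Under the section 8 rule most of the rate artefact goes (RR 1.00, or 0.95 to 1.03 at a 5% share with unequal propensity). But the Appendix does not carry that rule over: its own eligibility sentence and SoS definition say otherwise. In-scope comparators also leave the raw profiles of alerting inpatients drawn from different areas.

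A reader might go further and infer that scope pushes sex, age, ICU and mortality percentages in a known direction, or that the 0.01 threshold will be crossed with identical algorithms. The documents support neither. Four of the five scopes are not described, and ICHNT's is given only as current, not for February 2019 to January 2021. Crossing the threshold depends on an assumed share and assumed alert numbers. The chi-squared tests in section 3.1 also concern percentages of patients and subgroups who alert, not the sex split among those who did. Nor does ICHT contribute no young women: those alerting in its ED or other wards still count.

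**Conclusion.** The point holds as an unreconciled population rule and an unnamed source of bias. Under the Appendix rule, a narrow-scope Trust's SoS comparators and whole-Trust denominators count patients who could not alert. Under either rule, unadjusted profiles of alerting inpatients combine scope with algorithm.

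Size and direction cannot be taken from the documents. The illustration (RR 0.95 at a 5% share, 0.99 to 0.90 for 1% to 10%) rests on an assumed share, equal alert propensity and a whole-Trust denominator. It shows that a modest scope difference could pass for a modest algorithm difference, not that it will. The matter should be corrected before between-Trust differences are attributed to algorithms. It does not undermine within-Trust description or the ED rates.

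**What to change.** 1. Reconcile section 8 with Appendix section 2.2 (first study): state that SoS comparators and admission denominators are limited to each Trust's in-scope areas.
2. From Workstream 1, tabulate the areas and patient groups where each Trust's alert was live during the study period, 1 February 2019 to 31 January 2021.
3. Name alert scope in Appendix section 2.5 as a source of bias alongside case mix.
4. Add a between-Trust sensitivity analysis restricted to the scope common to all five alerts. Appendix section 2.7 says that only the ED versus inpatient split is consistently documented, with finer ward detail for some Trusts. Where ward type is missing, use an ED-only version, which every Trust can supply.

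The full local-scope tables can stay as the main description. The cost is a little extra analysis, and fewer alerts from broad-scope Trusts in the sensitivity analysis. A mandatory ward filter on every table is not proposed, because the documents do not show that all five Trusts could apply one.

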9. STUDY ACTIVITIES

WorkStream 2

Data extraction □ Quality check □ Data cleaning □ Data analysis □ Presentation of results to co-investigators □ Write up of results and discussion

WorkStream 3

Recruitment

The study is multicentre, involving recruitment of participants from several NHS hospital trusts and from community settings.

We will use our existing networks within Trusts, to identify suitable contacts and ask them to identify eligible healthcare professionals. We will ask contacts to invite any individuals to the study by email and will ask them to send emails out to relevant group email lists within the trust, where applicable, to advertise the study.

We will ask contacts in NHS trusts to advertise the study to eligible patients. This will involve staff sharing study adverts with eligible patients either in person or by email. This will include advertising the study to any existing patient groups linked to trusts (e.g., an 'ICU survivors' group present in one Trust). Those inviting patients will be part of the existing care team who already have access to patient details. Patient details will not be shared outside of the existing care team prior to patients contacting the research team. We will also advertise the study in hospital waiting areas and wards where relevant. We will also seek to recruit patients and carers through community channels. This will include advertising the study through relevant organisations, (e.g., UK Sepsis Trust), on social media websites (e.g., Twitter, Facebook) and though research participation websites (e.g., www.bepartofresearch.nihr.ac.uk). Potential participants will be asked to contact the research team if they are interested in joining the study.

Informed Consent

Written versions of the Participant Information Leaflet (PIL) and (Informed Consent Form) ICF will be provided to participants in advance of an interview or focus group. Potential participants will be allowed as much time as they wish to consider the information, and the opportunity to question the Investigator or other independent parties to decide whether they will participate in the study. At the start of the interview, the researcher will ask if the participant has any questions or would like to clarify any aspect of the PIL or consent. It will be clearly stated that the participant is free to withdraw from the study at any time for any reason without prejudice to future care, and with no obligation to give the reason for withdrawal.

Informed consent will be taken at the start of interviews, either verbally if an interview is carried out remotely or taken as written consent for interviews carried out in person. Informed consent for focus groups will be taken either in person at the start of focus groups or prior to virtual focus groups, where each participant will be telephoned and asked to give verbal consent. A written record of any verbal consent will be made by the interviewer. The researcher will sign and date written consent forms and the written records of verbal consent and will email a copy to the participant. All records of consent will be retained electronically on the University of Oxford computer network.

The person who obtained the consent must be suitably qualified and experienced and have been authorised to do so by the Principal Investigator.

Screening and Eligibility Assessment

A member of the research team will assess potential participants eligibility to take part in the research when they receive expressions of interest in response to emails and study adverts and when potential participants are identified by NHS trusts. Each participant must satisfy all the approved relevant inclusion and exclusion criteria of the protocol.

Subsequent Visits

Participants will take part in one interview or focus group. Health care professionals taking part in an interview may also be observed at work but they, as an individual, will not be followed up.

Discontinuation/Withdrawal of Participants from Study

Each participant has the right to withdraw from the study at any time without giving a reason. Any data collected from that participant up to point of withdrawal will still be included in analysis. Participants who withdraw will not be replaced once recruitment has ended. The Investigator may discontinue a participant from the study at any time if the Investigator considers it necessary for any reason including:

- Ineligibility (arising during the interview)
- Withdrawal of Consent

The reason for withdrawal by researcher (and by participant, if this information is volunteered) will be recorded in a study file.

Definition of End of Study

The end of study is 31st March 2023 at which point all study data will have been collected.

10. ANALYSIS

WS2 – Description of Analytical Methods

Detailed statistical plans are included in Appendix 1.

WS3 - Description of Analytical Methods

Data from interviews, focus groups and field notes from observations will be analysed inductively using thematic analysis.³²⁻³³ Thematic analysis allows the research team to take a pragmatic approach to data collection, remaining grounded in the data but ensuring that the analysis answers the research objectives. NVivo 12 software will be used to assist with the organisation and coding of data. We will support the rigour and trustworthiness of the analysis by triangulating healthcare professional and patient data to get a fuller understanding of how sepsis is managed in hospitals. We will assess the transferability of findings by comparing findings across the several Trusts taking part in the research and will describe the context of each Trust in detail to help establish what is common and different in findings between contexts. Confirmability will be established by making clear records of processes involved in data analysis and ensuring that findings can be tracked back to the original source(s).

To inform analysis we will collect data on healthcare professionals' sex, job role, years of experience in current role, and clinical expertise. We will collect data on patients' and carers' sex, age, nationality and ethnicity.

11. DATA MANAGEMENT

WS2 - Access to Data

Data will be stored in the Trusted Research Environment provided by Imperial College Healthcare Trust. All data transferred to the Research Informatics Team at ICNHT will be deidentified. Outside of this team only [name] will have access to the data.

WS3 - Access to Data

The Investigators listed on the title page will have direct access to the data. Direct access will be granted to authorised representatives from the Sponsor or host institution for monitoring and/or audit of the study to ensure compliance with regulations.

WS3 - Data Recording and Record Keeping

Each interview and focus group will be audio recorded with the participant's permission. Recordings will allow verbatim transcription in Microsoft Word. Audio recordings will be labelled with anonymous identifiers (IDs) and will be stored in a restricted-access folder on the University of Oxford computer network. Audio recordings will be deleted at the end of the study. Transcription will be completed by an independent transcriptionist/transcription company who holds a contract with the University of Oxford. Transcripts will be labelled with anonymous IDs and any identifiable data (e.g., identifying the participant(s) or their place of work) will be removed from the transcripts.

Participant characteristics will be entered on a separate Microsoft Excel spreadsheet with unique participant IDs only. Observation field notes will be stored as Word documents with unique site IDs and no mention of individual hospital staff so that Trusts cannot be identified. Participant characteristics, field notes and anonymised transcripts will be stored as Excel or Word documents a study folder with access restricted to the study team.

Transcripts will be uploaded to NVivo 12 software to aid analysis.

Names and contact details of participants will be kept in a password-protected document until the end of the study and then deleted. Electronic copies of ICFs, which contain participants' names, will be stored in password-protected files in a restricted-access study folder on the University of Oxford network and the Institute of Cancer Research network. Transcripts, field notes and ICFs will be stored securely for 10 years following the end of the study at the University of Oxford and the Institute of Cancer Research.

12. QUALITY ASSURANCE PROCEDURES

The study may be monitored, or audited in accordance with the current approved protocol, relevant regulations and standard operating procedures.

13. ETHICAL AND REGULATORY CONSIDERATIONS

Declaration of Helsinki

The Lead Investigators will ensure that this study is conducted in accordance with the principles of the Declaration of Helsinki.

Approvals

For WorkStream 2, the Sponsor will be the Institute of Cancer Research. The Health Regulator Authority (HRA) has confirmed that the study does not need formal review by a research ethics committee, as the study will only retrospectively use routine collected clinical data in anonymous

and aggregated form. The study has received HRA approval, which is now being amended due to a change in sponsor form Imperial College to the Institute of Cancer Research.

For WorkStream 3, the Sponsor will be the University Oxford. Following Sponsor approval the protocol, informed consent forms, participant information sheets, invitation letters/emails and any advertising material will be submitted to an appropriate Research Ethics Committee (REC), HRA (where required), and host institution(s) for written approval.

The Investigators will submit and, where necessary, obtain approval from the above parties for all substantial amendments to the original approved documents.

Other Ethical Considerations

There are no additional, specific ethical considerations.

Reporting

Lead Investigators will report regularly to the Con-Investigators and the Steering Committee. We shall submit once a year throughout the study, or on request, an Annual Progress report to the REC Committee, HRA (where required), host organisation and Sponsor. In addition, an End of Study notification and final report will be submitted to the same parties.

Participant Confidentiality

WS2 - This project utilises an established data de-identification and data sharing protocol developed by the NIHR Health Informatics Collaborative. A data specification and dictionary will be specified, defining the secure data transport mechanisms, patient cohort, data model, each data point to be collected (including standardisation and normalisation) and the steps to be taken at each site to ensure that appropriate de-identification is applied. This is signed off locally to enable legal transfer of the data (usually by the Caldicott guardian). The HIC provides support in this process via the informatics technical network of staff and a framework for data de-identification.

ICHNT have established secure infrastructure to enable data transfers (n3 256AES encryption) and secure data storage and analysis in the ICHNT NHS research data warehouse. The warehouse is fully secured and part of the ICHNT Data Security Protection Toolkit return, therefore can hold either de-identified or identifiable patient data

De-identified data will meet the expectations of the UK Information Commissioner's Office. In the case of clinical data, this will mean that: 1. any identifiers directly related to an individual (names, NHS numbers, hospital numbers, phone numbers, personal email addresses) will not be transferred between Trusts or shared with researchers. 2. Any spatial identifiers directly related to an individual (addresses and full postcodes) will not be transferred between Trusts of shared with researchers. 3. any elements of dates (except year) directly related to an individual (date of birth, date of admission, date of treatment, date of discharge, date of death) and all ages over 89 (and all elements of dates indicative of such ages) will not be transferred between Trusts or shared with researchers.

The originating centre will maintain a detailed record of the data transferred, including the mappings from original identifiers (in particular, the NHS number) to the de-identified version of the data. This means that the data transferred is de-identified, and that access to these mappings, as well as the overall information content of the data transferred, must be carefully controlled if the data is to be 'rendered anonymous' for the purposes of the General Data Protection Regulations (GDPR).

Where geographical information is required, one of two approaches may be adopted: a) the provision of a partial postcode, for example the first two outbound digits, common to approximately 200,000 households, or b) the provision of derived information required for the specific purpose, for example the English Index of Multiple Deprivation (IMD) 2015 Where temporal information is required, then a) only the year part of each date may be supplied, or b)

every date should be shifted by a randomly-chosen period of time, with the same period applied to each date pertaining to a particular individual, and that period being stored as part of the mapping from the direct identifiers for that individual to the data transferred.

Data will be stored in the Imperial College Healthcare NHS Trust (ICHNT) Clinical Analysis, Research and Evaluation (iCARE) platform. iCARE enables routinely captured clinical information to be appropriately utilised in research, evaluation and analysis within a highly secure Trusted Research Environment (TRE). The environment is approved by the ICHNT Caldecott Guardian, ICHNT Information and Communications Technology (ICT) team and ICHNT Data Protection offices for hosting and managing ICHNT patient level data for use in direct care and research. The environment is also approved by the Sector Caldicott Guardian and Information governance group to process data for the Whole Systems Integrated Care system for the purposes of COVID-19. The secure processing environment and the secure research environment are maintained on ICHNT infrastructure and cloud based platform hosted as a data processor by UKCloud. All infrastructure form part of the Trusts Data Security and Protection Toolkit, as prescribed by NHS Digital, and overseen by the Information Governance team of ICHT. The chief custodian is the Head of ICT at ICHNT. All ICHNT staff undertake annual data protection, information security and governance training, this includes all any researchers or analysts accessing the data. ICHNT have completed data protection privacy assessments on all processing in iCARE, and these are reviewed periodically. ICHNT information systems and external suppliers are subject to regular audits and independent reviews.

WS3 - The study will comply with the General Data Protection Regulation (GDPR) and Data Protection Act 2018, which require data to be de-identified as soon as it is practical to do so. The processing of the personal data of participants will be minimised by making use of a unique participant study number only on all study documents (except the ICFs and the document with participant names and contact details which will be password-protected and deleted at the end of the study) and any electronic database(s). All documents will be stored securely and only accessible by study staff and authorised personnel. The study staff will safeguard the privacy of participants' personal data.

Expenses and Benefits

Participation will be on a voluntary basis. If participants incur costs travelling to take part in focus groups, reasonable travel expenses will be reimbursed on production of receipts, or a mileage allowance provided as appropriate.

